Study Title: Study of Acarbose in Longevity

NCT02953093

IRB Number: 2016-6933

IRB Approval Date: 10/05/2018

Study of Acarbose in Longevity (SAIL)

A. Introduction and Specific Aims:

Acarbose, an FDA approved drug for the treatment of type 2 diabetes, has known effects on glucose metabolism. Evidence from mice indicates that acarbose may prolong lifespan. In humans, acarbose improves inflammatory markers and reduces cardiovascular events. Consequently, acarbose is of interest in clinical translational aging research since it may influence fundamental processes that contribute to age-related diseases. We herein propose an exploratory study to examine the effect of acarbose treatment on the biology of aging in humans. Specifically, we plan to investigate whether treatment with acarbose will restore the gene expression profile of older adults to that of young healthy subjects.

Specific Aims: We propose a 5 month randomized, double blind, placebo-controlled, cross-over study of acarbose treatment in older men (age > 60, n=30), with the following aims:

Specific Aim 1: To assess the effect of acarbose on gene expression profile, with a focus on molecular pathways known or suspected to play a role in aging.

Sub-aim 1: As a secondary analysis, we plan to assess the relationship between changes in gene expression with selected phenotypic variables and biomarkers, including changes in insulin sensitivity and glucose tolerance, vascular function, oxidative stress, inflammation, gut bacteria and/or serum microRNA profiles.

Specific Aim 2: To determine if treatment with acarbose will restore the gene expression profile of older, glucose intolerant men to that of young, healthy subjects.

B. Background and Significance:

Aging is a well-established risk factor for many disabling diseases including diabetes, cardiovascular disease, Alzheimer's disease and cancer. In fact, the risk of death from these causes is dramatically accelerated (100-1000 fold) between the ages of 35 and 85 years. There has been growing interest in understanding common pathways that accelerate age-related diseases, with the goal of therapeutically targeting such pathways to maintain health in older age. Several agents increase lifespan and prevent diseases of aging in animals, but studies in humans are needed.

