Acarbose, an FDA-approved diabetes medication, is one of the most promising anti-aging agents tested by the National Institute of Aging's Interventions Testing Program. Acarbose is a pseudotetrasaccharide of microbial origin, which lowers blood glucose primarily by inhibiting alpha-glucosidases, a group of enzymes that break down starch in the small intestine. This results in preferential absorption of carbohydrates at the lower small intestine, slowing of digestion time, and flattening of postprandial glucose and insulin excursions. Acarbose is primarily excreted in the feces, and approximately 1 % of acarbose is absorbed systemically, after undergoing fermentation. The string and st

In a recent study of genetically heterogeneous, non-diabetic mice, acarbose increased median lifespan by 22% in males and 5% in females.³ Maximum lifespan was increased by 11% and 9% in males and females, respectively, despite unchanged hemoglobin A1c

levels. Other notable effects include an increase in FGF-21, and decreases in weight, fasting IGF-1 and fasting insulin in acarbose-treated mice.³ In a follow-up study, acarbose started later in life (18 months) extended lifespan by 5% in male mice. Acarbose also improved age–related memory impairment in a separate mouse study.^{4,5} A study in diabetic rats showed that treatment with acarbose significantly altered the expression of miRNAs that target genes in the inflammatory pathways including interleukin 6 (IL-6), mitogen activated protein kinase 1 (MAPK-1) and tumor necrosis factor (TNF), primarily by acting through the MAPK pathway.⁴¹

In humans, treatment with acarbose has been shown to prevent the development of type 2 diabetes in high-risk individuals.⁶ In the STOP-NIDDM trial, acarbose also significantly decreased incident cardiovascular disease, including a decrease in myocardial infarctions.⁷ Subsequent studies, including a meta-analysis, have supported these findings,^{8,9} and a large clinical trial of acarbose for CVD prevention is currently underway in Asia.

¹⁰Treatment with acarbose is also associated with a decreased risk of colorectal cancer.¹¹ Taken together, these findings suggest that acarbose treatment may have pleotropic effects and support the need to study acarbose in human aging.

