The mechanism by which acarbose delays aging in mice is not established. Some authors have hypothesized that acarbose acts as a "caloric restriction mimetic." Caloric restriction (CR) is known to extend lifespan in some model organisms and healthspan in human and non-human primates. Although acarbose does not substantially lower net caloric exposure, like CR, it decreases fasting insulin and weight, improves glucose metabolism, and in mice, mimics some of the metabolomic changes seen with CR.^{2,3,6} ¹² In humans, acarbose has postprandial effects that include a decrease in lipids^{13,14} and inflammatory mediators, ¹⁵⁻¹⁷ an increase in postprandial nitric oxide and nitric oxide synthase¹⁸, and an improvement in endothelial function, suggesting that acarbose protects from adverse consequences of a prandial nutrient load. ¹⁹ However, it is not known whether such changes may contribute to the anti-aging effects of acarbose.

Acarbose also alters gut microbiota²⁰ and increases serum butyrate,²¹ a fermentation byproduct that is associated with improved glucose metabolism. Gut microbes are increasingly recognized as important mediators of inflammatory and metabolic processes in humans. With age, there is a change in gut microbial species, and certain profiles have been associated with frailty.^{22, 23} So the question naturally arises as to whether human gut microbiota directly influence aging, and if acarbose might alter this process. Acarbose also increases circulating postprandial GLP-1 levels by up to 50% and alters the secretion of other gut hormones, which might also contribute to its beneficial effects.^{24, 25} Finally, it is possible that the absorbed metabolites of acarbose have direct effects on tissues.

In summary, acarbose improves lifespan and age-related memory loss in mice and represents one of the most promising anti-ageing compounds tested by the Interventions Testing Program. In humans, it decreases the risk of certain age-related diseases, including diabetes, cardiovascular disease and colorectal cancer. It is an inexpensive, FDA-approved medication that has been used safely for many years. We hypothesize that acarbose might extend healthy lifespan in humans. As an initial step to test this hypothesis, we plan to study changes in gene transcription and a variety of biomarkers in older adults at risk for cardiometabolic disease.

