Informed consent	x							
		Diananaa		Diamanaa				
OGTT & eligibility labs (\$)	X	Dispense study meds (treat- ment A)		Dispense study meds (treat- ment B)		Start treatme nt B		
Safety monitoring (*)			X				X	
serum for miRNA				X				X
Stored samples for biomarkers,				Х				X

4	EINSTEIN				
Albert Einstein College of Medicine					

Vital signs, height, weight	Х	X	X	X		X	X
History	х	Interim history	Interi m histor y	Interim history		Interim history	Interim history
Physical exam (**)	X	X					
Standard meal test (#)				х			X
Muscle & adipose tissue biopsy				X			X
Fecal collection				Х			X

- (\$) eligibility labs include OGTT, Cr, AST/ALT, CBC, urinanalysis
- (*) safety monitoring includes recording of AEs and labs (Cr. AST/ALT)
- (#) standard meal test includes: fasting hsCRP, IGF-1, HbA1c and adiponectin, lipid profile, serum microRNA, Fasting and every 30 minute glucose, insulin levels.
- Fasting and 2 hour samples stored for possible future use.
- (**) Physical exam can be performed during visit 1 or visit 2.

Consent Process:

For this clinical investigation we will be consenting the research participants in compliance with our local IRB policy, Department of Health and Human Services (HHS) regulations for the Protection of Human Research Subjects (45 CFR 46) and FDA regulations (21 CFR 50 & 56).

For an initial phone screening we will be using a phone consent form that contains also HIPAA language. We will ask for permission to collect personal information and if they agree to be contacted for other future studies.

During the screening visits in the Clinical Research Center (CRC), subjects will sign the current IRB-approved and stamped consent document.

Prior to the adipose and muscle biopsies (visit 4 and visit 6), the physician performing the procedures will obtain consent using a standard Montefiore procedural consent, again detailing the procedures and expected risks.

Study visits:

Screening visit (Visit 1): Following informed consent, a history, vitals, anthropometrics, and screening labs, including OGTT, will be obtained.

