Visit 4: At the completion of the 10-week treatment period (up to 4 week titration, 6 week maximum dose) a standard mixed meal test (SMT) will be conducted and muscle and adipose tissue biopsies will be performed, after procedural risks are again explained by the physician performing the muscle and fat biopsies and a Montefiore procedural consent is signed by the participant. Fasting and 2hour blood samples will be collected for analyses noted above. Stool sample tubes will be collected. Vital signs and interval history will be obtained. Subjects will bring unused medication for assessment of adherence. Additional interim safety and/or adherence visits will be conducted if indicated. Instructions to maintain usual diet and activity patterns will be reinforced at each visit. Participants will be given treatment B, and will be instructed to start them after a 2-week washout. The same titration instructions detailed above will be provided to participants. Phone call- After a 2 week washout participants will be reminded to start treatment B with a phone call

Visits 5-6: The procedures in visits 3-4 will be repeated.

C.1.2 Inclusion and Exclusion Criteria:

[figure not shown]
Subjects with impaired glucose tolerance or with mild, untreated diabetes (defined below) based on a screening OGTT will be enrolled. Patients with a prior diagnosis of diabetes may enroll if they are not taking anti-diabetic medications and they meet OGTT criteria. If a participant has had an OGTT within the past year, results of this test may be used to determine eligibility. Given rodent studies demonstrating pronounced effects on males, we plan to recruit males for this small study, with a plan to study females in a subsequent, larger study if effects are seen. Although this approach decreases the generalizability of our initial findings, by increasing the homogeneity of the study population and targeting the gender most likely to benefit, we hope to improve the power to detect a treatment effect in this small, preliminary, study.

Inclusion:

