C.2.3 Specific Aim 2: To determine if treatment with acarbose will restore the gene expression profile of older, glucose intolerant men to that of young, healthy subjects. We hypothesize that transcriptional changes detected above may reflect some aspects of the transcription profiles of younger adults and provide insight into specific pathways affected by acarbose.

Under a separate protocol (2016-7110), young individuals aged 20-40 will be recruited and will undergo fat and muscle biopsies for RNA sequencing as detailed above. Changes

seen in the acarbose group in muscle and fat transcriptome will be compared to the young transcriptome, to identify aging-specific pathways affected by acarbose

C.3. Data analysis, rationale, limitations of experimental design:

C.3.1 Study design: We plan to conduct a double-blind placebo controlled trial with crossover design. The previous studies performed by our group (resveratrol and metformin) were cross-over studies with gene transcription data on 16 and 14 individuals, respectively. We identified clear differences in gene transcription profiles between resveratrol and placebo, using the same criteria outlined above. We expect that acarbose would have a similar if not larger effect size, thus 30 individuals in a crossover design is sufficient to detect differences. Data are still being analyzed for the metformin study. Cross-over study design is advantageous in terms of increased power for the study size. However, there is a risk for carryover effects since metabolic, transcriptional, and gut microbial changes may persist after the medication is cleared from circulation during the 2-week washout. Therefore, we plan to also separately analyze those who received treatment first in a sub-analysis to detect any long lasting changes that may result in a carry-over effect. Changes in physical activity and diet could confound interpretation of our metabolic studies, although the double-blind, placebo controlled study design will help to mitigate any potential impact. Changes in weight and body composition will also be carefully monitored. If there are significant changes in physical activity or weight, we will adjust for these in our data analysis.

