these specifically implement a splice-junction aware alignment protocol. Pair-wise correlation and principal component analyses on each sample's gene expression profile will be used to determine the quality of the experiment, identify batch effects and other systematics. Differential expression between samples (young and old, and after acarbose and after placebo) will be determined, using a negative binomial model approach such as that implemented in the DESeq package. Genes that show an adjusted p-value of less than 0.05 and a fold change greater than 2 will be selected for further scrutiny between placebo and acarbose conditions. Furthermore, our RNA-seq data will permit us to identify splice variants between the experimental conditions. The differential gene list will be processed with Ingenuity Pathway Analysis and GoStat, allowing us to identify dysregulated pathways and common gene ontology terms differentiating the acarbose transcriptome for the tissue types under scrutiny. Finally, the entire differential expression profile will be processed using the Broad's Gene Set Enrichment Analysis platform against over 10,000 curated gene lists, to provide additional regulatory perspectives on the data. These analyses are considered exploratory in nature and will be used to inform future tests that may target specific gene expression pathways. It will also allow us to make collaborative associations with phenotypes, although these associations will be complex considering the numerous potential age-delaying effects that may occur, some of which may be independent of the measured physiologic parameters.

Insulin sensitivity, biomarkers, etc.: Differences in mean acarbose vs. placebo treatment outcomes (insulin sensitivity, inflammatory biomarkers) will be tested for significance using paired t-test or Wilcoxon test (for non-parametric data). A two-tailed alpha level of 0.05 will denote statistical significance.

miRNA analysis:

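### The plan adjusts for on-treatment weight when it changes significantly, although it lists weight loss as an acarbose effect and does not make the unadjusted comparison the main result

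*Combined protocol and SAP*

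**What the plan says.** After discussing carryover, section C.3.1 notes that changes in activity and diet could confound the metabolic studies, "although the double-blind, placebo controlled study design will help to mitigate any potential impact". It says weight and body composition will be monitored, and then: "If there are significant changes in physical activity or weight, we will adjust for these in our data analysis". It does not define what counts as significant, which comparison is tested, what form the covariate takes, or which model is used.

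Section B says of acarbose: "Although acarbose does not substantially lower net caloric exposure, like CR, it decreases fasting insulin and weight". Its summary of the mouse lifespan study reports "decreases in weight, fasting IGF-1 and fasting insulin in acarbose-treated mice".

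Section C.3.2 tests acarbose against placebo for insulin sensitivity and inflammatory biomarkers with a paired t-test or a Wilcoxon test, two-sided at 0.05, and mentions no covariates. Sub-aim 1 in section A gives the phenotypic variables and biomarkers their place: "As a secondary analysis, we plan to assess the relationship between changes in gene expression with selected phenotypic variables and biomarkers".

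The C.1 schedule has a row for "Vital signs, height, weight" and none for physical activity. The Visit 4 text adds: "Instructions to maintain usual diet and activity patterns will be reinforced at each visit".

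**The concern.** In a randomised, blinded crossover, a systematic weight difference between the acarbose and placebo periods is, apart from imbalance caused by dropout, a drug effect or chance. It is not a confounder in the sense that would justify adjustment. Section B goes further and offers weight loss as part of the idea that acarbose mimics caloric restriction, so weight may belong to the mechanism under study.

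Adjusting for it changes the question. The unadjusted paired difference estimates the whole effect of acarbose. The usual adjusted one compares the treatments at equal weight. If the trigger is the acarbose-placebo weight difference, the rule is most likely to fire when acarbose does lower weight, which is when the two questions differ most. Insulin sensitivity and inflammatory markers plausibly respond to weight, so a real effect could be reported as smaller than it is, or as absent. C.3.2 also says the data will be used to estimate effect size for later studies, without saying for which outcomes. An estimate whose target was chosen by a test on weight is a poor input for that.

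**Working it through.** **No figure to reproduce.** The plan's 30 participants come with no effect size, SD or power. What follows is an illustration, and every numerical input except n = 30 and the 0.05 level is an assumption.

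**What adjustment estimates.** Let D_W be the acarbose-minus-placebo weight difference within a man and D_Y the outcome difference, scaled to SD 1 with benefit positive. With z and e independent standard normal:

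- D_W = -m + 1.5z (mean loss m kg, SD 1.5 kg)
- D_Y = 0.55 - rz + sqrt(1 - r²)e (r is the correlation between weight loss and benefit)

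The total effect is 0.55, close to the 0.53 SD that 30 pairs detect with 80% power. Regressing D_Y on D_W and reading the intercept gives the effect at equal weight:

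- adjusted effect = 0.55 - r × m/1.5
- share mediated, if r reflects mediation = r × m/(1.5 × 0.55)

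For m = 1 and r = 0.2, the adjusted effect is 0.55 - 0.2 × 0.667 = 0.417. Because no model is named, even this is not fixed: centring D_W at its mean would return the unadjusted 0.55.

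**Cost in precision.** The unadjusted standard error is 1/sqrt(30) = 0.183. With r = 0 the adjusted one is roughly 0.183 × sqrt(1 + (1/1.5)²) = 0.22 at m = 1, because the intercept lies away from the observed mean weight difference. Power is lost even with no mediation.

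**The rule.** Take the adjusted result if a t-test on D_W has p < 0.05, otherwise the unadjusted paired t-test. Simulation, 500,000 trials per row; unadjusted estimate 0.55 and power 83% throughout. The last column is the share of trials significant unadjusted but not under the rule.

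| m (kg) | r | Mediated | Rule fires | Mean estimate | Power | Significance lost |
|---|---|---|---|---|---|---|
| 1 | 0 | 0% | 94% | 0.55 | 66-67% | 18% |
| 1 | 0.08 | 10% | 94% | 0.50 | 58% | 26% |
| 1 | 0.21 | 25% | 94% | 0.42 | 46% | 37% |
| 0.5 | 0.2 | 12% | 42% | 0.51 | 73% | 10% |
| 0.3 | 0.2 | 7% | 18-19% | 0.53 | 79% | 4% |

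**Not a clean direct effect either.** If r = 0.2 arises only from a shared cause of weight and outcome, with no mediation and m = 1, the total and weight-independent effects are both 0.55, yet the adjusted estimate is still 0.42 (200,000 trials). The trial's data cannot separate this from the mediated case.

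**Type I error.** With no effect on weight or outcome, and correlations of 0.3 to 0.7 between the two differences, the conditional rule rejects in 3.7% to 4.5% of trials, so it does not inflate the error. Reporting whichever of the two results is significant would give 6.2% to 8.1%.

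**The case against.** The strongest reply is that the plan never says the adjusted result replaces the paired test. C.3.2 names one biomarker test with its alpha level, and the adjustment sentence closes a paragraph on design limitations. It could be read as a supplementary contingency. If both results were always reported with the paired test first, no significance would be lost. That is a possible reading, but the sentence says the data analysis itself will be adjusted, and no text puts the paired test first.

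Other points limit the size of the problem:

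- **Trigger.** A significant change could mean drift over the 22 weeks, not a treatment difference. If the treatments do not differ in weight, adjustment removes nothing on average: with 0 kg and r = 0.2, the estimate stays at 0.55, power at 83%, and 0.5% of trials lose significance. A different trigger changes how often the rule fires, not what ordinary adjustment does when acarbose does lower weight.
- **Direction.** With r = -0.2 and 1 kg, the rule gives 0.68 and 84% power. Understatement therefore depends on weight loss going with benefit. That is plausible for these outcomes, but the documents do not establish it.
- **Dropout.** Men who tolerate no study medication are withdrawn, and a paired test without a period term could pick up weight drift if completers are unbalanced by sequence. This is a fair qualification, but the remedy is a period term, not adjustment for weight.
- **Inputs.** The evidence on weight is one mouse result and one unquantified general clause, in a sentence that also says net caloric exposure is not substantially lowered. For r from 0 to 0.21, the mean shifts of 0 to 0.13 SD are below one trial's standard error of 0.18.
- **Scope.** The outcomes most clearly concerned are secondary, and gene expression is affected only if the rule is applied there.

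These points bound the size. They do not remove the defect, which is a stated rule that can substitute a different effect for the effect of acarbose.

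**Conclusion.** The concern holds. As written, the plan can exchange the total effect of acarbose for an equal-weight effect on the strength of a weight test, using a variable that it says acarbose changes. The consequence is minor to moderate. It is a matter of what is estimated and of lost power, not of inflated type I error under the rule itself.

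The size cannot be fixed from the documents. It depends on the human weight effect, its SD, how far weight and outcome move together, and whether the adjusted result becomes the reported one. Under the assumed inputs it runs from a four-point loss of power (0.3 kg, r = 0.2) to a fall from 83% to 46% (1 kg, a quarter mediated). Confidence is medium: the textual conflict is plain, but its practical effect rests on those assumptions. The activity half of the rule has a separate gap, since the schedule provides no measure of activity to apply it with.

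**What to change.** Replace the adjustment sentence in C.3.1 with: *The main acarbose-versus-placebo comparisons will not be adjusted for post-randomisation weight, body composition or physical activity. Weight-adjusted results will be reported as a secondary, explanatory analysis, whether or not the weight change is significant.*

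Name the model for that secondary analysis, including how the weight difference enters and whether it is centred. If activity is to be used, name the measure and the visits. The wording should cover gene expression as well as the metabolic outcomes, because the present sentence is not limited to either. Including body composition closes the same route for a variable that C.3.1 already monitors.

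The cost is one sentence and one secondary analysis. Weight is already in the visit schedule, so that part needs no new data, and the investigators keep the adjusted result they wanted.

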Muscle and adipose are key metabolic tissues that undergo significant age-related changes, and play an active role in the pathogenesis of aging. ²⁷⁻²⁹ We are characterizing transcriptional changes with aging in these tissues, and studying the effects of therapeutic interventions. RNA-Seq analysis is being used to identify pathways targeted by candidate anti-aging drugs that have been tested in animals. In addition, we are accumulating a repository of muscle and adipose biopsy samples obtained from young healthy controls to establish a unique biological "fingerprint" for aging in these tissues by comparing changes in gene expression in older adults, post-drug therapy to the profiles of young healthy subjects. This overall approach is supported by a grant from the Glenn Foundation for the Study of the Biology of Human Aging and we are currently analyzing data from two prior studies using metformin and resveratrol. We have gene transcription profiles from RNA seq performed on fat and muscle biopsies from 4 young individuals and plan to recruit up to 30 more young participants under a separate protocol.

As part of our secondary analyses, we also plan to assess changes in microRNA levels in the serum. MicroRNAs (miRNAs) are small, non-coding RNAs that regulate gene expression at a post-transcriptional level. Due to their stability in blood, changes in expression of circulating miRNA might serve as markers for age-related pathologies. Investigators at Einstein have profiled B-lymphocyte miRNA levels in the plasma and have identified microRNA profiles associated with exceptional longevity. We hypothesize that acarbose treatment will alter the expression of circulating miRNAs in a way that may offer insight into anti-aging mechanisms of acarbose. Given the known effects of acarbose on colonic fermentation and composition of gut microbiota we plan to explore changes in gut microbiome using 16s rDNA seq. We plan to correlate changes in transcription (muscle and fat RNAseq), post-translational regulation (miRNA) and gut microbiome with changes in clinical metabolic outcomes and inflammatory biomarkers.

C. Research Methods:

C.1. Study Design & Protocol Summary: We propose a 22-week randomized, double-blind, placebo controlled cross-over study of acarbose in older adults (n=30) with impaired glucose tolerance.

		Treat-			Wash	Treat-		
		ment A			-out	ment b		
	Visit 1	Visit 2 0	Visit 3 4 wks	Visit 4 10 wks	2 wks	Phone call: 12wks	Visit 5 16 wks	Visit 6 22 wks

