C.3.2 Statistical analysis and sample size: We plan to enroll up to 30 older male subjects in a cross-over design (30 data points per treatment). Since this is an exploratory study, data obtained will be used to design future interventions that are larger in size and include women, and/or that more specifically investigate pathways that may be affected by acarbose. Data from this study will also be used to estimate effect size and to allow formal power calculations for future, larger studies. Previous studies of gene transcription have demonstrated that effect sizes on gene transcription can be substantial,³⁵ and differential expression can be detected in the same tissues, before and after an intervention in as few as 10-15 individuals.³⁶ Our study of resveratrol confirms the ability to detect differential expression in a sample size of 16, using a crossover design even when clinical effects are modest or negligible. Increasing the sample size to up to 30 will increase the ability to detect transcripts with a lower fold change.

RNA-Seq: Transcriptional profiles will be obtained by the use of the RNA-Seq assay at Einstein's Sequencing Core Facility, specifically using multiplexed 100bp single-end sequencing on an Illumina HiSeq2500. Under a separate protocol, #07-534, we have analyzed transcripts of muscle and adipose tissues obtained from unrelated young (20-30 yo) and we plan to submit another protocol to recruit additional young controls whose transcriptional profiles will further expand our "repository". These analyses will help us further define the parameters of biological transcript changes with aging. These results will provide "proof of concept" and help to set the stage for testing more interventions.

We anticipate $\sim 30M$ reads passing quality control to be aligned to the human genome. The alignment process will be implemented by use of the GSNAP and HTSeq packages – [version date 9/30/18]

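### Aim 2 young-versus-old contrast: the 4 young profiles already sequenced are tied to an earlier run, and nothing commits the new young controls to shared runs or the model to a run term

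*Combined protocol and SAP*

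**What the plan says.** Two sources of young profiles are described.

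- **Existing.** Section B: "We have gene transcription profiles from RNA seq performed on fat and muscle biopsies from 4 young individuals". The RNA-Seq part of C.3.2 also reports young tissue (ages 20 to 30) already analysed under protocol 07-534. It gives no number there, and these may be the same 4 people.
- **Still to come.** Section B: "plan to recruit up to 30 more young participants under a separate protocol". Section C.2.3, which describes Aim 2, says "young individuals aged 20-40 will be recruited and will undergo fat and muscle biopsies for RNA sequencing as detailed above", under protocol 2016-7110. C.3.2 says "we plan to submit another protocol to recruit additional young controls", to expand a repository of young profiles.

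The trial contributes up to 30 older men with one sample per treatment. The visit schedule in C.1 places their biopsies at visits 4 and 6. C.3.2 names one core facility, one platform and multiplexed sequencing, but does not allocate samples to library batches, lanes or runs.

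C.3.2 mentions batch once: pair-wise correlation and principal components will be "used to determine the quality of the experiment, identify batch effects and other systematics". It then tests young against old, and acarbose against placebo, with a DESeq-type negative binomial model. It names no run term, bridging samples or correction step.

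**The concern.** Profiles that already exist were made in a different run from trial samples that the protocol describes as still to be collected. If all young samples sit in one set of runs and all older samples in another, a technical difference between runs looks exactly like an age difference. Genes shifted by library preparation or sequencing would be listed as ageing genes. Aim 2 asks whether acarbose moves older men's expression towards the young profile, so its reference would be contaminated. Principal components would show a clear separation without saying what caused it, and no later analysis recovers the age effect from such a layout.

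**Working it through.** The plan states no power, dispersion or batch size for Aim 2, so there is no figure of its own to reproduce. The check has three parts. It assumes the older group is the 30 placebo samples, because C.3.2 does not say which older samples enter the young-versus-old test.

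**1. Can age be estimated apart from run?** Take a model with an intercept, an age term and one term per additional run. Age is estimable only if at least one run holds both age groups.

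| Layout | Rank / columns | Age estimable with a run term? |
|---|---|---|
| 4 existing young only; 30 older in trial runs | 2 / 3 | No |
| 4 existing, plus 30 new young in their own run | 3 / 4 | No |
| 4 existing, plus 30 new young co-run with the 30 older | 3 / 3 | Yes |
| 4 existing with 4 older samples in the earlier run (assumed), no new young | 3 / 3 | Yes |

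In the first layout the age and run columns are identical. A shift caused by age and the same shift caused by run give the same data, hence the same first principal component (R² with the shared indicator 0.996 either way).

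**2. Bias and precision.** Without a run term, the young-minus-old difference absorbs the run shift multiplied by the fraction of young samples in the other run.

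- 4 existing only: 4/4 = 100%.
- 4 existing plus 30 co-run: 4/34 = 11.8%.
- 4 existing plus 10 or 5 co-run: 4/14 = 29% or 4/9 = 44%.

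With a run term the bias in the co-run layouts is zero. The 4 earlier profiles then add nothing, since their run holds no older sample. In units of the within-group SD:

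- All 34 young pooled, no run term: SE = √(1/30 + 1/34) = 0.250.
- 30 co-run young, run term: SE = √(1/30 + 1/30) = 0.258, about 3% larger.
- 10 or 5 co-run young, run term: √(1/30 + 1/10) = 0.365 or √(1/30 + 1/5) = 0.483.
- No new young, but 4 older samples in the earlier run (assumed): √(1/4 + 1/4) = 0.707.

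**3. How many false age genes?** Simulation with 15,000 genes, no true age effect, 30 older men, person SD 0.6 log2, two-sample t tests and Benjamini-Hochberg adjustment at 0.05. Each gene has its own run shift, with SD 0.3 or 0.5 log2. All SDs are assumptions. Approximate mean counts:

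| Layout | Shift SD 0.3 | Shift SD 0.5 |
|---|---|---|
| 4 existing young alone | 90 | 1,900 |
| 30 young, all in separate runs | 3,500 | 7,500 |
| 4 existing pooled with 30 co-run, no run term | under 1 | under 1 |

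With no run shift the counts are below 1. If more than a two-fold change is also required, the 30-separate counts fall to about 45 and 830, and the 4-alone counts to about 80 and 1,300. At adjusted p<0.05 alone, a larger separately run young group makes matters worse, because the shift is estimated more precisely.

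**The case against.** A reader might infer that Aim 2 as a whole is confounded with batch. The documents do not support that. C.2.3 describes a prospective young group, which could supply up to 30 of 34 young samples (88%). The shared core facility and multiplexed platform allow these to be run with the trial samples, and no section says they will be run apart. If about 30 are co-run, pooling in the 4 earlier profiles does essentially no harm even without a run term. The large counts therefore depend on a layout the documents do not state.

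Other limits also stand:

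- Even for the 4, coincidence of age and run assumes that no older samples shared the earlier run and that no stored RNA is re-sequenced. The group's resveratrol and metformin studies also have transcription data, and the documents do not say which runs those samples used.
- The two-fold filter is stated for acarbose against placebo. No rule is given for young against old, and applying the filter there cuts the counts sharply.
- The simulation uses t tests rather than the negative binomial model.
- C.3.2 calls the analyses exploratory, and protocol 2016-7110, not seen here, may specify library handling.

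None of this supplies a safeguard in this plan. Exploratory status does not make an inestimable contrast informative, and the layout has to be fixed before sequencing.

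**Conclusion.** The point holds as a conditional risk to one of the two specific aims. For the 4 existing profiles, age and run coincide, subject to the two exceptions on which the documents are silent. For the young-versus-old contrast as a whole, confounding is complete if only those 4 are used or if the new controls are sequenced separately. It is essentially absent if about 30 new controls are co-run with the trial samples. The plan does not commit to any of these, and its one batch step can detect a shift but not attribute it. The rank results need no assumed SDs; the gene counts are illustrative and rest on the assumed person and batch SDs. The acarbose-placebo contrast lies within the older men, does not use the young samples and is not affected. A change to the plan is warranted because it is cheap beforehand and, short of re-sequencing, cannot be made afterwards.

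**What to change.** In C.3.2:

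1. Require the new young libraries to be prepared and sequenced interleaved with the trial's placebo and acarbose libraries, so that every library batch and run holds both age groups.
2. Include run in the young-versus-old model.
3. Base the Aim 2 contrast on those samples, and use the 4 earlier profiles only in a sensitivity analysis. If their stored RNA is available, re-sequencing it in the shared runs would let them count.
4. State the gene-selection rule for young against old.
5. Reconcile the young age range (20 to 40 in C.2.3, 20 to 30 for the earlier samples in C.3.2) and the status of the new young protocol (numbered in C.2.3, still to be submitted in C.3.2).

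The cost is scheduling, and possibly holding libraries until both groups are available. Leaving the 4 out of the main contrast raises its SE from 0.250 to 0.258 SD if 30 new controls are obtained. Precision falls further if fewer are recruited, but the estimate then still measures age rather than run.
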